2. INTRODUCTION

Note: in this document any text taken directly from the protocol is *italicised*.

Pancreatic neuroendocrine tumors (NET) are rare malignancies with an incidence of approximately 2.5 to 5 cases per 100,000 per year. For patients with metastatic disease, the 5-year survival rate is low, and cure is generally not possible.

Pancreatic neuroendocrine tumors are highly vascular tumors. Investigation of angiogenesis inhibitors such as sunitinib and everolimus in patients with pancreatic NET is therefore of great interest. Results from a Phase 2 study of sunitinib (RTKC-0511-015) demonstrated activity, which was confirmed in a Phase 3 study (A6181111). Based on these results, sunitinib was approved for the treatment of unresectable or metastatic, well-differentiated pancreatic neuroendocrine tumors with clinical trial waiver by China Food and Drug Administration (CFDA) in Nov. 2012.

There is currently lack of systematic collection and analysis for the efficacy and safety data of sunitinib in Chinese patients with progressive, unresectable, advanced or metastatic well-differentiated, pancreatic neuroendocrine tumors. The sunitinib non-interventional (NI) study is designed to collect data systematically and to assess the safety and efficacy in Chinese patients with progressive, unresectable, advanced or metastatic well-differentiated, pancreatic neuroendocrine tumors. It is designed and conducted to meet CFDA post-marketing commitments. One of post marketing commitments was “Please carry out a post-marketing observational study on the indication in pancreatic Neuro-Endocrine Tumors. A detailed and strict protocol should be designed to collect the data on safety and efficacy from every patient. Data on survival rate should be collected for at least 5 years”.

2.1. Study Design

This study is a multi-center, prospective, non-interventional (NI) study evaluating the safety and efficacy of CFDA approved sunitinib in Chinese patients with progressive, unresectable, advanced or metastatic well-differentiated, pancreatic neuroendocrine tumors.

Approximately 100 adults with progressive advanced or metastatic well-differentiated unresectable pancreatic neuroendocrine tumors will be recruited in China hospitals. Each subject will be followed up overall survival (OS) time or the date of withdrawal and subjects who remain alive after study completion will have their OS time censored on the last date known to be alive. The dosage of sunitinib is based on individual safety and tolerability in daily clinical practice. Subjects will be treated until disease progress, unacceptable toxicity, withdrawal of subject consent or other withdrawal criteria are met. Subjects with evidence of disease progression may continue on treatment if judged to have clinical benefit.

Baseline data include demographic data, medical history, medication history, physical examination, 12-lead Electrocardiogram (ECG), hematology and blood chemistry. If applicable, tumor imaging will also be collected. For the subjects who have already taken sunitinib within the past 6 months (26 weeks) and will continue sunitinib therapy, these key element baseline data will be collected prior to their sunitinib treatment after the subject or their legal representative has provided informed consent. For the subjects who haven't taken sunitinib and will accept sunitinib therapy, they (or a legally acceptable representative) sign on current Institutional Review Board (IRB)/Independent Ethics Committee (IEC) approved informed consent document.

During treatment period, data collection includes administration of sunitinib, physical examination, 12-lead ECG, hematology and blood chemistry. If applicable, the following will be collected: Multiple gated acquisition (MUGA) or Echocardiography (ECHO) for Left Ventricular Ejection Fraction (LVEF) assessment, thyroid function testing, urine protein assessment and tumor imaging. Safety data collected throughout the treatment period will consist of all Adverse Event (AE) and Serious Adverse Event (SAE) data. For the subjects who have already taken sunitinib within the past 6 months (26 weeks) and will continue sunitinib therapy, they (or a legally acceptable representative) sign on current Institutional Review Board (IRB)/Independent Ethics Committee (IEC) approved informed consent document on the day that they decide enrollment this study.

During the post-treatment follow-up visit, if applicable, the following will be collected: hematology, blood chemistry, thyroid function testing and physical examination within 28 days (+10 days) after the end of treatment or study withdrawal. The concomitant medications and treatments including antineoplastic therapies will be recorded. The outcome of adverse events with a date of onset during the study period should be reevaluated. All serious adverse events, and those non-serious adverse events assessed by the investigator as possibly related to study drug should continue to be followed even after subject withdrawal from study. These adverse events should be followed until they resolve or until the investigator assesses them to be "chronic" or "stable".

Survival follow-up includes progression free survival, PFS by clinical judgment and overall survival. All subjects will be followed for tumor progression (Computerized Tomography (CT)/Magnetic Resonance Imaging (MRI) or clinical judgment) and overall survival (OS) time or the date of withdrawal. Subjects who remain alive after study completion will have their OS time censored on the last date known to be alive.

2.2. Study Objectives

The sunitinib non-interventional (NI) study is a real world observational study which represents the usual and customary treatment of patients and is being proposed to collect data systematically and to assess the safety and efficacy in Chinese patients with progressive, unresectable, advanced or metastatic well-differentiated, pancreatic neuroendocrine tumors.

Primary Objective

- *To evaluate the safety profile of CFDA approved sunitinib in treating Chinese patients with progressive, unresectable, advanced or metastatic well-differentiated, pancreatic neuroendocrine tumors.*

Secondary Objectives

- *To assess progression-free survival (PFS);*
- *To assess PFS by clinical judgment;*
- *To assess overall survival (OS);*
- *To estimate 5-year survival rate.*

3. INTERIM ANALYSES, FINAL ANALYSES AND UNBLINDING

Two interim analyses are planned to deliver interim reports to CDE before 15 Mar 2017 and some day in year 2022 for license renewal. The interim analyses will include all the data and analyses that will be reported in the final analysis.

Final analysis will be conducted after the official database is released.

Unblinding is not applicable for this study as it is a non-interventional single arm study, and no DMC is needed.

4. HYPOTHESES AND DECISION RULES

4.1. Statistical Hypotheses

This study is non-comparative and no inferential statistical analyses are planned. Analyses will consist of descriptive statistics and corresponding 95% 2-sided confidence intervals when appropriate.

4.2. Statistical Decision Rules

There are no statistical decision rules.

5. ANALYSIS SETS

5.1. Full Analysis Set

The Full Analysis Set (FAS) will be defined as all patients who receive at least one dose of study drug during the study. All efficacy analyses will be performed using the FAS.

5.2. ‘Per Protocol’ Analysis Set

Not applicable.

5.3. Safety Analysis Set

The safety population will be defined as all enrolled patients who take at least one dose of the study drug; all summaries of safety will be reported within the safety analysis set. The safety analysis set is the same as full analysis set in this study.

5.4. Other Analysis Sets

Not applicable.

5.5. Treatment Misallocations

Not applicable.

5.6. Protocol Deviations

Protocol deviations (minor/major) will be compiled prior to database closure and will be listed for the FAS.

6. ENDPOINTS AND COVARIATES

6.1. Efficacy Endpoint(s)

All efficacy endpoints are secondary endpoints in this study. Default start date is date of first treatment during the study, if the date is not available, date of enrollment will be used.

6.1.1. Progression-Free Survival

Investigator assessed PFS according to RECIST 1.1. PFS is defined as the time from start date to first document of objective tumor progression or death due to any cause, whichever occurs first. PFS (in months) will be calculated as (first event date — start date +1)/30.44.

PFS data will be censored on the date of the last objective tumor assessment on study for subjects who do not have objective tumor progression and who do not die while on study. Patients with documentation of a PFS event after an unacceptably long interval (>17 weeks) since the previous objective disease assessment will be censored at the date of the previous assessment. Patients with no on-study objective disease assessments are censored at the start date unless death occurred within 17 weeks post first dose (in which case the death is an event). Patients with inadequate baseline disease assessment are censored at the start date. Adequate baseline is defined using the following criteria:

- Subjects with target lesions: All target lesions had measurement(s) within the baseline window (200 days) and measurable.
- Subjects with non-target lesions only: All non-target lesions had non missing assessments(s) and at least one of the non-target lesions assessed as non-indeterminate within the baseline window (200 days).

Additionally, subjects who start a new anti-cancer therapy prior to Progressive Disease (PD) will be censored at the date of the last tumor assessment prior to the start of the new therapy.

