6.1.2. Progression-Free Survival by Clinical Judgment

PFS by clinical judgment is defined as the time from start date to first document of objective tumor progression, or first time tumor progression diagnosed by investigator based on clinical judgment, or death due to any cause, whichever occurs first. PFS by clinical judgment (in months) will be calculated as (first event date – start date +1)/30.44.

PFS by clinical judgment data will be censored on the date of the last tumor assessment on study for subjects who do not have tumor progression (objective or based on clinical judgment) and who do not die while on study. Patients with documentation of a PFS by clinical judgment event after an unacceptably long interval (>17 weeks) since the previous disease assessment (objective or based on clinical judgment) will be censored at the date of the previous assessment. Patients with no on-study disease assessments (objective or based on clinical judgment) are censored at the start date unless death occurred within 17 weeks post first dose (in which case the death is an event). Additionally, subjects who start a new anti-cancer therapy prior to Progressive Disease (PD) will be censored at the date of the last tumor assessment prior to the start of the new therapy.

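### The 17-week gap rule for PFS does not say whether the baseline scan counts; read literally, it can censor first-scan progression at or before the start date

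*SAP*

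**What the plan says.** SAP 6.1.1 sets the gap rule: "Patients with documentation of a PFS event after an unacceptably long interval (>17 weeks) since the previous objective disease assessment will be censored". The censoring date is that of the previous assessment. Three nearby provisions matter:

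- On the age of the baseline scan, for patients with target lesions: "All target lesions had measurement(s) within the baseline window (200 days) and measurable". The window for non-target lesions is also 200 days. The date from which the 200 days count back is not given.
- On patients never scanned on study: "Patients with no on-study objective disease assessments are censored at the start date unless death occurred within 17 weeks post first dose". A death inside that window counts as an event.
- On the time variable: "PFS (in months) will be calculated as (first event date — start date +1)/30.44".

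SAP 6.1.2 has the same gap rule for PFS by clinical judgment, counted "since the previous disease assessment (objective or based on clinical judgment) will be censored at the date of the previous assessment". It has no adequate-baseline criterion and no 200-day window.

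SAP 6.1 starts the clock at first treatment during the study. Protocol 8.2.5 admits patients who have already taken sunitinib within the past 26 weeks, and Protocol 8.3.1 takes their baseline data from before that treatment. Protocol 8.3 fixes no visits.

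**The concern.** The gap sentence leaves open what the previous assessment is when the first on-study scan is read. Two features of the wording let baseline in. The gap sentence lacks the on-study qualifier that the sentences before and after it carry. The SAP also calls baseline a disease assessment: "Patients with inadequate baseline disease assessment are censored at the start date".

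If baseline counts, a scan that 6.1.1 accepts as adequate can already be older than the gap limit on the day treatment starts. Progression at the first on-study scan is then removed as an event and given a censoring date before the clock starts. These are among the fastest progressions. Patients who are stable at the same scan stay at risk, so any error makes PFS look better. Two programmers following the same SAP could report different medians.

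**Working it through.** The plan states no figure on this point, so there is none to reproduce.

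**When the rule bites.** Let b be the days from baseline scan to start date, and d the days from start date to first on-study scan. The limit is 17 × 7 = 119 days, and 200 − 119 = 81 days of the baseline window lie beyond it. If baseline counts, progression at the first scan is censored when b + d > 119.

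- b = 28: only if d > 119 − 28 = 91.
- b = 60: only if d > 119 − 60 = 59.
- b ≥ 119: at any scan after the start date.

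**The censoring time.** Applying the SAP's formula to the baseline date gives (−b + 1)/30.44 months:

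- b = 28: −27/30.44 = −0.89
- b = 100: −99/30.44 = −3.25
- b = 200: −199/30.44 = −6.54

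**Prior users.** They may have had up to 26 × 7 = 182 days of sunitinib before enrolment. A baseline taken just before that gives (−182 + 1)/30.44 = −5.95 months on the SAP's clock. A scan made on sunitinib before enrolment, if it counts, shortens the gap but still lies before the SAP start date. This extra exposure depends on the SAP's start date; the protocol counts from the start of sunitinib treatment.

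**Share of first-scan progressions removed.** With b uniform on 0 to W, the share is max(0, W − (119 − d))/W.

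| First scan | W = 60 | W = 90 | W = 200 |
|---|---|---|---|
| Week 8 (d = 56) | 0 | 27/90 = 30% | 137/200 = 69% |
| Week 12 (d = 84) | 25/60 = 42% | 55/90 = 61% | 165/200 = 83% |

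**Effect on the median.** I simulated 300,000 patients with exponential PFS (median 11.4 months, the Phase 3 sunitinib arm in Protocol section 6), progression found at scans with varying intervals, and no other censoring. Scan intervals and baseline ages are assumptions.

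| Scan interval | Gap rule not applied | W = 60 | W = 90 | W = 200 |
|---|---|---|---|---|
| 7-9 weeks | 12.6 | 12.6 | 12.9 | 13.3 |
| 10-14 weeks | 13.1 | 13.9 | 14.2 | 14.8 |

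The largest shift is 14.8 − 13.1 = 1.7 months. With W = 30 the shift is 0 (7-9 weeks) or 0.2 months (10-14 weeks). Across the table, 0 to 7% of all patients lose an event with 7-9-week scans and 7 to 13% with 10-14-week scans. Six-month PFS with 10-14-week scans rises from about 0.73 to about 0.78, 0.81 and 0.84.

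A separate run with scans exactly every 112 days lost events in 18 to 20% of patients, and six-month PFS rose from 0.800 to between 0.971 and 1.000. The median there moved by 0 or 3.6 months, because it can fall only on scan dates.

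**Would a programming patch cure it?** Resetting the negative times to day 1 as censored gives the same medians as dropping the records. Either way these patients leave the risk set before the first event. The harm lies in the lost events as well as in the invalid times.

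**The case against.** The strongest reply is that the SAP never says baseline counts. The sentence on patients without an on-study scan counts 17 weeks from first dose and censors at the start date, and Protocol 8.7 also censors patients with no post-start evaluation at the start of treatment. If the previous assessment means an on-study one, these rules agree. This stands: the fault is an ambiguity with a biased literal reading, and it would be wrong to report it as a stated rule.

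A reader might infer more than the documents support:

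- **That every first-scan progression is lost.** It is lost only when b + d > 119. Recent baselines with early scans lose nothing.
- **That early failures in general drop out, or that the SAP contradicts itself on deaths.** Take a death at week 10 with no on-study scan and a baseline 8 weeks before first dose. The gap rule alone would censor it (10 + 8 = 18 weeks), but the specific sentence makes it an event, and a specific rule normally governs. Only the order of the rules is unstated.
- **That 6.1.2 has the same 200-day clash.** It has no baseline window, and assessments by clinical judgment also count as previous there. It shares only the undefined anchor and the missing floor.
- **That the new-therapy rule routinely censors before the start.** A patient with no on-study scan is censored at the start date. An earlier date can arise only when the first on-study scan comes after the new therapy.

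On size, 200 days is a maximum, and nothing in the documents suggests that baseline ages spread evenly up to it. With 100 patients, the simulated median under 10-14-week scans, without the rule, has a 95% sampling range of roughly 10 to 16 months, wider than any shift in the table. That tempers the importance. It does not excuse a one-directional error that can be avoided.

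**Conclusion.** The concern holds as an ambiguity that should be closed. On the literal reading of SAP 6.1.1, progression at the first on-study scan is censored at or before the start date whenever baseline age plus scan day exceeds 119. Prior users, whom SAP 8.1 also reports as a separate group, are most exposed under the SAP's start date.

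Any bias is upward: 0 to about 1.7 months in the median for baseline ages spread over 0-60 to 0-200 days and scans every 7 to 14 weeks, and potentially more with sparser scans. These sizes rest on assumed scan intervals, baseline ages and an exponential curve; they show a range and are not a forecast. PFS is secondary, the analysis is descriptive and there is no decision rule, so this is a should-fix.

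**What to change.** Add to SAP 6.1.1 and 6.1.2:

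1. For the first on-study assessment, or a death before it, the 17-week interval is measured from the start date and not from the baseline scan.
2. Any censoring date earlier than the start date, including one produced by the new-therapy rule, is set to the start date.
3. The rule for patients with no on-study assessment takes precedence over the gap rule.

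This matches the SAP's existing death rule and keeps progression at any first scan up to day 119 as an event. Progression at a later first scan would still be censored, but at (0 + 1)/30.44 = 0.03 months and not at a negative time.

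The cost is a few sentences and one programming condition. PFS may look slightly less favourable than under the literal reading.

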8.3.5. Survival Follow-up

Survival follow-up includes progression-free survival, PFS by clinical judgment and overall survival.

All subjects will be followed for tumor progression (CT/MRI or clinical judgment) and overall survival (OS) time or the date of withdrawal. Subjects who remain alive after study completion will have their OS time censored on the last date known to be alive.

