8.2.2. Analysis of Secondary Efficacy Endpoints

Secondary efficacy endpoints will be summarized for the FAS.

For secondary efficacy time-to-event endpoints (PFS, PFS by clinical judgment and OS), the Kaplan-Meier method will be used to obtain the estimates of median event-free time. Confidence intervals for the 25th, 50th and 75th percentiles of the event-free time will be reported based on the sign test (Brookmeyer and Crowley 1982, produced with “PROC LIFETEST” in SAS). Some time-to-event endpoints will be displayed graphically when appropriate. Sensitivity analyses will be conducted for efficacy endpoints by excluding patients with major protocol deviations.

For 5-year survival rate, the estimate and 95% confidence interval will be calculated from the Greenwood method (produced with “PROC LIFETEST” in SAS).

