9. APPENDICES

Appendix 1. DATA DERIVATION DETAILS

Appendix 1.1. Derivation of PFS by Clinical Judgment

The following is the IOTA CRF page:

INVESTIGATOR OVERALL OBJECTIVE TUMOR ASSESSMENT - RECIST (VERSION 1.1)			IOTA003
 (1) NOT DONE			
Date of Tumor Assessment (dd-MMM-yyyy):  -  - 			
Tumor Assessment			
Target Lesions (check (X) ONE only):			
 (0) No Target Lesion At Baseline			
 (1) Complete Response		 (2) Partial Response	
 (4) Progressive Disease		 (5) Not Assessed	
 (3) Stable Disease		 (6) Indeterminate	
Non Target Lesions (check (X) ONE only):			
 (0) No Non-Target Lesion At Baseline			
 (1) Complete Response		 (3) Progressive Disease	
 (5) Indeterminate		 (6) No Complete Response/No Progressive Disease	
New Lesion:			
 (1) Yes			
 (2) No			
Overall (check (X) ONE only):			
 (1) Complete Response		 (2) Partial Response	
 (4) Progressive Disease		 (5) Not Assessed	
 (3) Stable Disease		 (6) Indeterminate	

VARIABLE INFORMATION:

OPTIONAL INFORMATION:

DESIGN GUIDELINE: This page should not be used for RECIST 1.0 assessments.

This DCM should be deployed at post-baseline/screening assessments.

Place the IOTA page in a CPE separate from the general cycle information. If the tumor assessment schedule is based on weeks from randomization, use weeks in the CPE label. If the tumor assessment schedule is based on cycles, cycle may be used in the label, but it should be placed in its own CPE.

On the IOTA page, if “Not Assessed” is checked for both Target Lesions and Non Target Lesions, no option is checked for New Lesion, and “Progressive Disease” is checked for Overall, then tumor progression diagnosed by investigator based on clinical judgment is reached on the Date of Tumor Assessment.

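### Both PFS endpoints censor every patient who starts a new anti-cancer therapy before progression; no planned analysis varies this rule, and as worded it can give a negative PFS time.

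*SAP*

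**What the plan says.** SAP 6.1.1 counts two kinds of event: "PFS is defined as the time from start date to first document of objective tumor progression or death due to any cause, whichever occurs first". It then censors early switchers: "subjects who start a new anti-cancer therapy prior to Progressive Disease (PD) will be censored at the date of the last tumor assessment" before that therapy. The reason for the switch plays no part. Protocol 8.7 has the same rule for both PFS endpoints.

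SAP 6.1.2 widens the event to include "or first time tumor progression diagnosed by investigator based on clinical judgment, or death due to any cause, whichever occurs first". Appendix 1.1 derives this from the investigator's tumor assessment (IOTA) page: if target and non-target lesions are marked not assessed, the new-lesion item is blank and the overall result is progressive disease, "then tumor progression diagnosed by investigator based on clinical judgment is reached on the Date of Tumor Assessment". SAP 6.1.2 still repeats the censoring rule: "Additionally, subjects who start a new anti-cancer therapy prior to Progressive Disease (PD) will be censored at the date of the last tumor assessment" before the switch. It does not say whether PD there includes progression by clinical judgment.

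The only efficacy sensitivity analysis, in SAP 8.2.2, is this: "Sensitivity analyses will be conducted for efficacy endpoints by excluding patients with major protocol deviations". Protocol 8.3.5 states: "All subjects will be followed for tumor progression (CT/MRI or clinical judgment) and overall survival (OS) time or the date of withdrawal". Protocol 8.1 adds that further antineoplastic therapy and time to death are collected after treatment stops.

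**The concern.** Kaplan-Meier treats a censored patient as having the same outlook as those still at risk. Protocol 8.3 fixes no visits, imaging is done where applicable in routine practice, and Protocol 8.9 concedes that imaging timing and progression standards will vary. A patient who is failing may therefore change therapy before a scan documents it. The rule then removes that patient at the last good scan, and the failure never counts. Switching under routine care is not in itself a protocol deviation, so the planned sensitivity analysis does not test the rule.

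The second problem is one of wording. The general censoring sentence in SAP 6.1.1 refers to the last objective assessment on study; the new-therapy sentence drops that limit. Read literally, it can point to a pre-treatment scan.

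At stake are the PFS medians and intervals in the final report and in the interim reports that SAP 3 ties to license renewal.

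**Working it through.** **Inputs.** The documents give no switching rate, scan interval or planned median PFS for this study. The 11.4 months in Protocol 6 (sunitinib arm of the Phase 3 study) serves only as an anchor. Assumed: exponential time to progression; for the simulation, scans every 2 to 4 months (uniform, random phase); a share *q* of progressing patients switched at true progression, before the confirming scan.

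**Hand check, switching for failure.** If a share *q* of failures is censored instead of counted, the observed hazard falls by the factor (1 - *q*), so the median becomes 11.4/(1 - *q*): 12.7, 14.3 and 16.3 months for *q* = 10%, 20% and 30%.

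**Simulation with scan delay.** With no switching the Kaplan-Meier median is 12.9 months, because progression is dated at the next scan. Repeat runs differ by about 0.1 month.

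| *q* | Rule as written (no clinical PD recorded) | Half recorded as clinical PD (clinical-judgment PFS) | Switch counted as event | Rule minus event |
|---|---|---|---|---|
| 10% | 14.0 | 13.3 | 12.8 | 1.2 |
| 20% | 15.3 | 13.8 | 12.6 | 2.7 |
| 30% | 17.0 | 14.4 | 12.5 | 4.5 |

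If every such failure is recorded as clinical PD by the time of the switch, clinical-judgment PFS equals the switch-as-event column.

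**Switching unrelated to prognosis.** With progression dated exactly, 2-month assessments used only to back-date the censoring, and 10%, 20% or 30% switching for independent reasons, the rule gives 11.3, 11.3 and 11.1 months against a true 11.4. There is no inflation. Counting those switches as events gives 11.4 x (1 - *q*) = 10.3, 9.1 and 8.0 months, which is too low.

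**Ignoring the switch instead.** This uses the first later progression or death. With an assumed 12-month median delay from the switch to that event, the medians are 14.1, 15.3 and 16.7 months, almost the same as under the rule. With a 24-month delay they are 14.4, 16.2 and 18.3, above the rule. The SAP also censors any event more than 17 weeks (17 x 7/30.44 = 3.9 months) after the previous assessment. With delays of 6 to 24 months and no further scans, 75% to 93% of the later events would be sent back to the same pre-switch scan.

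**Negative time.** Take a patient with an adequate baseline who switches before the first on-study scan and is scanned afterwards.

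1. The rule for patients with no on-study assessments does not apply, because a later scan exists.
2. The last assessment before the new therapy is the baseline scan. SAP 6.1.1 allows a 200-day baseline window, taken here as days before the start date.
3. Applying the SAP formula to the censoring date, (date - start + 1)/30.44: a scan 60 days earlier gives (-60 + 1)/30.44 = -1.9 months; one 200 days earlier gives (-200 + 1)/30.44 = -6.5 months.

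Patients already on sunitinib are the most exposed. Protocol 8.3.1 takes their baseline from before their original treatment, while SAP 6.1 dates the start from first treatment during the study.

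**The case against.** A reader might infer that median PFS is overstated, and that nothing in the plan would show it. The documents support neither statement.

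Overstatement requires that switching marks failure. The rule covers any switch; Protocol 9.2 lists unacceptable toxicity among the reasons for stopping, and Protocol 8.1 allows sunitinib to continue after progression. No switching rate is given, and the simulation takes the worst case by placing every switch exactly at progression. This part of the objection stands, so the size is illustrative.

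PFS by clinical judgment is pre-specified and counts recorded clinical progression, so comparing the two curves shows part of the effect. That stands too. What remains are patients switched for failure with neither objective nor clinical PD recorded, who are censored in both endpoints. There is also a wording gap: if PD in SAP 6.1.2 were read as objective PD only, the endpoint would censor the very patients it was designed to capture.

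An analysis that simply ignores the switch might look like the natural remedy. The figures above show that it can agree with the main result and falsely reassure, so it is not the recommended check.

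The negative time is an edge case, and a programmer might well read on-study into the sentence. But the written rule yields an impossible value, and nothing in the documents says how to handle it.

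**Conclusion.** The concern holds in a limited form. Every switch before PD is censored in both PFS endpoints, and no planned analysis varies that. If 10% to 30% of progressing patients are switched before the confirming scan and none is recorded as clinical PD, the median is inflated by about 1.2 to 4.5 months. The inflation shrinks as clinical PD is recorded and disappears if switching is unrelated to prognosis. These figures rest on the assumed switching shares, scan interval, exponential shape and 11.4-month anchor. The direction depends only on whether switching is informative, which the documents do not settle.

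The negative censoring time follows from the wording and needs no assumption about why patients switch. How often it would arise is unknown.

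Severity is modest. Efficacy is secondary, the study is non-comparative with no decision rule, and no formal comparison with the Phase 3 median is planned.

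**What to change.** 1. In SAP 6.1.1 and 6.1.2, censor at the last on-study tumor assessment before the new therapy or at the start date, whichever is later.
2. In SAP 6.1.2, state that PD includes progression by clinical judgment as derived in Appendix 1.1.
3. Keep the main rule. In SAP 8.2.2, add for both PFS endpoints a sensitivity analysis that counts the start of new anti-cancer therapy as an event on its start date. State that the 17-week rule does not apply to that event. Report the number of patients the rule censors.
4. An analysis ignoring the switch is optional. Include it only if the 17-week rule is lifted for it and its limits are stated: it absorbs any benefit of the next therapy and depends on scanning after the switch.

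A split by reason for switching is not requested. Protocol 9.2 records a reason for stopping treatment, its list has no progression category, and no reason for starting the next therapy is mentioned.

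**Cost.** SAP wording, one more Kaplan-Meier run per PFS endpoint and one count. The date of new therapy is already needed for the existing rule. Under Protocol 8.7 the SAP may modify the planned analyses, and only major changes to the primary endpoint call for a protocol amendment. The downside is that counting every switch as an event understates PFS when switches are for toxicity, so the result belongs beside the main estimate as a lower bound and does not replace it.
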